### 6.3 SURGICAL PROCEDURES

For subjects in open surgical treatment arm: A transverse incision is made at the distal palmar crease overlying the affected digit. Blunt dissection proceeds down to the level of the A1 pulley and the pulley is incised under direct visualization. The surgical site will then be irrigated and closed in usual fashion.

For subjects endoscopic treatment arm: The proximal interphalangeal crease is identified of the affected finger and incised transversely. Blunt dissection is then performed down to the level of the pulley. With the finger held in extension, the EndoSleeve is inserted from distal to proximal at a 15 degree angle. The A1 pulley is visualized via the endoscope. The tip of the EndoSleeve is then situated on the distal edge of the A1 pulley. As the tip is advanced proximally, the blade is seen incising the A1 pulley. The instrument is advanced to a point just before the distal palmar crease. The surrounding tissue is then inspected and the instrument removed. The surgical site is then irrigated and closed in usual fashion.

### 6.4 MEDICAL IMAGING

Photographs of the affected hand will be taken per medical photographic standards pre-operatively, on the day of surgery, and 1 week, 1 month, and 6 months post-op as is the standard of care.

A copy of any medical imaging results (e.g., hand radiology) collected during the study duration will be included in the study file. No radiographic imaging is required for the study.

### 6.5 INSTRUCTIONS FOR THE SUBJECTS

There are no special instructions for the subjects beyond those typically provided for hand surgery and in the informed consent. Subjects will be asked to complete the POSAS questionnaire at 1 week, 1 month, and 6 months post-operatively.

### 6.6 UNSCHEDULED VISITS

Each time the subject returns to the study site the Investigator will solicit and record information about any concurrent procedures or AEs as applicable though not anticipated.

## 7 STUDY INTERVENTION DISCONTINUATION AND PARTICIPANT DISCONTINUATION/WITHDRAWAL

### 7.1 EARLY DISCONTINUATION OF SUBJECTS

Each subject reserves the right to withdraw from the study at any time without jeopardy to their future medical care. All follow-up assessments and procedures should be performed at the final study visit. For any subject who discontinues from the study, the date and reason for discontinuation will be recorded.

If a subject fails to return for one or more scheduled study visits, the Investigator will attempt to contact the subject to determine and document the reason the subject has failed to return and to encourage compliance with the study visit schedule.

A subject may be discontinued from the study for the following reasons:

- Subject did not undergo surgical treatment as it was deemed not warranted by the Investigator
- Since enrollment in the study, subject has had alternative treatment that would otherwise affect the study questionnaire/outcomes data
- Subject does not complete scheduled follow-up visits per protocol
- Subject has died

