#### 4.3 DURATION

Subjects will be followed for 6 months post-operatively. POSAS scores will be obtained at 1 week, 1 month, and 6 months post-operatively. These scores along with measures of pain medication use, days before return to work, and duration of OT will be obtained from each subject during their post-operative visit. Complication and recurrence rates will also be noted at each post-operative visit. Study visits will coincide with standard clinical course visits.

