### 8.1.2 SECONDARY OUTCOME MEASURES

Secondary outcome measures include pain medication use, overall patient satisfaction (score 1 to 10), days to return to work, and duration of post-operative occupational therapy as well as complication and recurrence rates after endoscopic versus open surgical treatment. Complications will include injury to tendons, nerves, and digital vessels noted during or after surgical treatment, as well as surgical site dehiscence and surgical site infections requiring antibiotics. Recurrence will be defined as triggering, confirmed on physical exam by treating physician, at any time point post-operatively.

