## 9 STATISTICAL PROCEDURES

Every attempt will be made to collect complete data and limit the occurrence of missing data. Due to the descriptive nature of all analyses, no imputation of missing data will be performed. Descriptive summaries will be based on all observations available within each of the relevant analysis populations.

Descriptive statistics will be presented for key outcome measures.

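### The missed-visit contact in 7.1 collects no outcomes, and no procedure captures triggering treated elsewhere, so recurrence can be understated and late patient-reportable data lost

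*Combined protocol and SAP*

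**What the plan says.** Outcome collection is tied to clinic visits. Under 4.3, the POSAS, pain medication use, time to return to work and duration of occupational therapy (OT) "will be obtained from each subject during their post-operative visit". The same section adds: "Complication and recurrence rates will also be noted at each post-operative visit". Section 6.1.3 repeats the visit-based collection of the POSAS and the recovery measures at 1 week, 1 month and 6 months.

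For a missed visit, 7.1 says that "the Investigator will attempt to contact the subject to determine and document the reason the subject has failed to return". The sentence continues with a second purpose, so that the aim of the contact in full is "to determine and document the reason the subject has failed to return and to encourage compliance with the study visit schedule". For early leavers, 7.1 also says: "All follow-up assessments and procedures should be performed at the final study visit".

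Sections 8.1.2 and 9.2.2 define the event identically: "Recurrence will be defined as triggering, confirmed on physical exam by treating physician, at any time point post-operatively".

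Two of the grounds on which 7.1 allows discontinuation are alternative treatment that would affect the outcome data and failure to complete the visits. Section 9.1 then leaves discontinued subjects out of the analysis. Section 9 states that "no imputation of missing data will be performed" and bases the summaries on the observations available. Sections 4.1, 5.1 and 9.6 allow extra enrolment after death or withdrawal to reach 12 per arm.

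**The concern.** Absence from a visit after a minor hand operation is plausibly related to recovery. One kind of absentee is well and back at work. Another still has triggering and has gone to a different clinician. The study team may reach both by telephone under 7.1, yet the plan asks neither for an outcome.

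Most of what is missed could be reported in that call: return-to-work date, days of OT, pain medication use, satisfaction, triggering, further treatment of the digit and complications. The POSAS Patient Scale is completed by the subject (6.2) on paper (8.3), so it could be filled in at home.

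Recurrence is the most exposed outcome. A subject treated elsewhere for persistent triggering has no written procedure by which the event is obtained, and that same treatment is a possible ground for discontinuation and hence exclusion. A treatment failure could thus remove itself from the failure rate. Sections 1.1 and 9.3 anticipate no significant difference between arms in complications or recurrence, and lost events make that expectation easier to appear to meet.

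**Working it through.** **Inputs.** From the documents: 12 subjects per arm and 24 in total (1.1, 5.1, 9.6); the recurrence definition (8.1.2, 9.2.2); discretionary discontinuation (7.1); exclusion of discontinued subjects (9.1); no imputation (section 9). Assumed, because the documents give no figure: the number of recurrences, and a missed-visit rate of 10–20%.

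**1. The plan's own figure.** For a POSAS difference of 10, SD 8, two-sided 5% and 80% power, the normal approximation is n = 2(1.96 + 0.84)² × 8²/10² ≈ 10.05, so 11 per arm. The two-sample t-test solution is 11.09, so 12 per arm, with power 83.3% at 12. The plan's figure reproduces and is not in dispute; it supplies the denominator below.

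**2. What happens to one true recurrence treated elsewhere.** Take x true recurrences among n treated in an arm, one of them not captured.

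- True rate: x/n.
- Subject discontinued and excluded: (x − 1)/(n − 1).
- Subject retained without a recorded event: (x − 1)/n.

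| x of 12 | True | Excluded | Retained, no event |
|---|---|---|---|
| 1 | 1/12 = 8.3% | 0/11 = 0% | 0/12 = 0% |
| 2 | 2/12 = 16.7% | 1/11 = 9.1% | 1/12 = 8.3% |

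The error is 8.3 points for x = 1 on either route. For x = 2 it is 16.7 − 9.1 = 7.6 points or 16.7 − 8.3 = 8.3 points (2/12 − 1/12 = 1/12).

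**3. Does losing a well subject balance this?** If the excluded subject had no recurrence, 1/12 becomes 1/11: 9.1 − 8.3 = 0.8 points upward. Losing one recurrence therefore shifts the rate about ten times as far as losing one well subject (8.3 against 0.8 points). The net direction depends on who is lost.

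**4. Does replacement repair it?** If the excluded subject counts as withdrawn and is replaced by one without recurrence, 13 have been treated and the true rate is 1/13 = 7.7%. The analysis reports 0/12. The count is restored; the event is not.

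**5. How many subjects.** 10% of 24 = 2.4 and 20% of 24 = 4.8, so about 2 to 5 subjects missing a given visit under the assumption.

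**6. Side effect on the POSAS comparison.** Without replacement, t-test power falls from 83.3% at 12 per arm to 79.6% at 11 and 75.3% at 10. Home completion of the Patient Scale would not restore a total score, because the Observer Scale would still be missing.

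**The case against.** Four stronger readings are tempting, and the documents do not support them.

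- A reader might infer that the contact serves only to record a reason. It also aims to bring the subject back, and a subject who returns can be assessed. What stands is that encouragement yields no data from a subject who still does not come.
- A reader might infer that a subject who goes elsewhere is scored as free of recurrence. No rule says so. The written route is discretionary discontinuation (7.1) followed by exclusion (9.1). A retained subject with earlier negative examinations could in practice be tabulated without an event, but that is a possibility, not a provision.
- A reader might infer that a missed visit loses everything. Subjects are asked to self-report adverse events (8.2), so some complications may still arrive. Return to work and OT duration are asked repeatedly and may be complete by 1 month. Recurrence counts at any time, so persistent triggering can be confirmed at a later attended visit.
- A reader might infer that an outside clinician's finding can never qualify. The term treating physician is not defined, so this is not certain. Either way, no procedure obtains such findings.

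It can also be said that requiring an examination is a sound choice for specificity, and that the analyses are descriptive and exploratory. The first is a good reason to leave the definition alone. The second limits the consequence, but a descriptive recurrence rate is still misleading if failures leave the denominator.

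**Conclusion.** The point holds in a limited form. As written, the plan makes contact with subjects who miss visits but takes no outcomes from them, provides no means of capturing triggering seen or treated elsewhere, and allows such subjects to be discontinued and so excluded. That can understate recurrence and loses late patient-reportable data, chiefly at 6 months.

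Each lost recurrence costs about 8 percentage points in an arm of 12. This is an illustration of scale, not a prediction: the documents give no recurrence or missed-visit rate, and the 2 to 5 subjects rest on the assumed 10–20%. Downward bias is conditional on at least one absentee having recurred. The change is worth making because the contact is already planned and the remedy is inexpensive.

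**What to change.** **7.1.** Use the planned contact to collect return-to-work date, days of OT, pain medication use, overall satisfaction, triggering, any further treatment of the study digit, and complications. Send the POSAS Patient Scale for completion at home. Offer the same to subjects who stop visits but agree to be contacted.

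**8.1.2 and 9.2.2.** Keep the exam-confirmed recurrence definition. Add a separate tabulation by arm of reported triggering, or re-treatment of the study digit by any clinician.

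**9.1.** Keep treated subjects who are discontinued for missed visits or alternative treatment in the full analysis population, with whatever data were obtained, and report by arm the number whose recurrence status is unknown. Without this change, a recurrence learned of by telephone could still be discarded on discontinuation. Because 9.1 makes the per-protocol population primary, show the recurrence table for the full analysis population as well.

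**Cost.** A short call script, a mailed form and wording in four sections; no added visit. Reported events are less certain than examined ones, which separate display makes visible. The Observer Scale stays missing for that visit. The amendment needs IRB approval (Statement of Compliance), and obtaining outside records may need authorization that 10.1.2 does not describe beyond imaging.

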## 8 OUTCOME MEASURES AND SUMMARY OF METHODS OF DATA COLLECTION

### 8.1 OUTCOME MEASURES

#### 8.1.1 PRIMARY OUTCOME MEASURE

Primary outcome measures include scarring based on Patient and Observer Scar Assessment Scale (POSAS) scores administered 1 week, 1 month, and 6 months post-operatively between patients treated with endoscopic versus open surgical release of the A1 pulley.

### 8.1.2 SECONDARY OUTCOME MEASURES

Secondary outcome measures include pain medication use, overall patient satisfaction (score 1 to 10), days to return to work, and duration of post-operative occupational therapy as well as complication and recurrence rates after endoscopic versus open surgical treatment. Complications will include injury to tendons, nerves, and digital vessels noted during or after surgical treatment, as well as surgical site dehiscence and surgical site infections requiring antibiotics. Recurrence will be defined as triggering, confirmed on physical exam by treating physician, at any time point post-operatively.

### 8.1.3 EXPLORATORY MEASURES

- Operative time

## 8.2 SAFETY MEASURES

The incidence and severity of AEs related to the study will be captured. Investigators will inquire about the occurrence of any AEs at all study visits and unscheduled visits. Subjects will also be asked to self-report AEs throughout the duration of the study. Adverse events will be recorded.

## 8.3 SUMMARY OF METHODS OF DATA COLLECTION

Paper documents will be used to collect standardized assessments for POSAS scores. Study-specific information, such as Investigator reviews and assessments will be recorded directly in the subject's medical record.

Pain medication use, days before return to work, duration of OT, complications, and recurrences will be recorded by the Investigator in the subjects' medical record.

Operative time will be obtained from the operative record within the patient's electronic medical chart, as recorded by operative staff.

## 9 STATISTICAL PROCEDURES

Every attempt will be made to collect complete data and limit the occurrence of missing data. Due to the descriptive nature of all analyses, no imputation of missing data will be performed. Descriptive summaries will be based on all observations available within each of the relevant analysis populations.

Descriptive statistics will be presented for key outcome measures.

### 9.1 POPULATIONS FOR ANALYSES

All subjects will be included in the full analysis population. The per protocol population is defined as subjects who have not had any major protocol deviations throughout the study (Section 9.8) and will be analyzed as the primary study group. Other subgroups may be analyzed as detailed in the subgroup analyses section. Subjects that have been discontinued will be excluded from data analysis.

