#### 6.1.1 PROCEDURES FOR FINAL STUDY ENTRY

A subject is considered "enrolled" when he/she has signed the IRB-approved consent form and HIPAA authorization in the presence of the Investigator, who will then collect and record the subject's demographic information and medical history.

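### Section 9.1 includes every subject in the full analysis population and then excludes every discontinued subject, so valid 1-week and 1-month POSAS scores can be discarded

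*Combined protocol and SAP*

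**What the plan says.** Section 9.1 opens with "All subjects will be included in the full analysis population". It then defines a per-protocol population, free of major deviations, which "will be analyzed as the primary study group". It ends with "Subjects that have been discontinued will be excluded from data analysis". Sections 9.3 to 9.5 do not say which population any analysis uses.

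Section 7.1 permits, but does not require, discontinuation for listed reasons. Besides death, these are:

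- incomplete follow-up, worded as "Subject does not complete scheduled follow-up visits per protocol";
- treatment received outside the plan, worded as "Since enrollment in the study, subject has had alternative treatment that would otherwise affect the study questionnaire/outcomes data";
- no operation, because the investigator judges that surgery is not needed.

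The same section says "All follow-up assessments and procedures should be performed at the final study visit", and asks the investigator to try to contact subjects who miss visits. Under 6.1.1 a subject is enrolled "when he/she has signed the IRB-approved consent form and HIPAA authorization in the presence of the Investigator", which is before surgery.

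POSAS at 1 week, 1 month and 6 months is the primary outcome (8.1.1). It is summarised at each visit (9.3.1) and tested at each visit by exploratory t-tests (9.5). Recurrence counts whenever it occurs after surgery (8.1.2). Section 9 rules out imputation and bases summaries on the observations available within each analysis population.

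**The concern.** A population cannot contain all subjects and also omit the discontinued ones. If the last sentence of 9.1 governs, no analysis set contains everyone, and the full set differs from per-protocol only by subjects who stayed in the study despite a major deviation.

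What is at stake is data already in hand. A subject seen at 1 week and 1 month, and then discontinued for missing month 6, drops out of all three visit summaries. The plan asks for assessments at exit and then has no use for them. If leaving is related to how the patient fared and differs by arm, the early comparisons are also biased, in a direction that depends on which arm loses patients. The event rates are exposed too, because with 12 per arm a single removed subject can change a reported rate to zero.

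**Working it through.** **1. The plan's own figure.** Section 9.6 gives a difference of 10, SD 8, two-sided 5% and 80% power. The normal approximation is 2 × 8² × (1.960 + 0.842)² / 10² = 10.05, which rounds up to 11. The t-test calculation gives 11.09, which rounds up to 12, with power 83.3% at 12 per arm. The stated 12 per arm is reproduced and is not in question.

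**2. Does another section limit the exclusion?** The available-observations rule in Section 9 works only within a population, and 9.1 has already removed the subject from it. Sections 9.3 to 9.5 name no set. Nothing confines the exclusion to per-protocol or to visits after discontinuation.

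**3. Scores lost.** Let k of 12 subjects in one arm miss only month 6 and be discontinued (k is assumed). Each has 2 valid scores, so 2k are discarded and n at 1 week and 1 month is 12 − k. At 6 months n is 12 − k with or without the rule.

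**4. Shift in the arm mean at 1 week or 1 month.** Shift = ρ × SD × s, where ρ is the assumed correlation between exclusion and score. The factor s is the mean shift, in SD units, when the k most extreme of 12 normal scores are removed: 0.15, 0.28 and 0.39 for k = 1, 2 and 3. SD = 8 is from 9.6. At ρ = 0.5:

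- k = 1: 0.5 × 8 × 0.15 = 0.60
- k = 2: 0.5 × 8 × 0.28 = 1.12
- k = 3: 0.5 × 8 × 0.39 = 1.56

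Direct simulation (400,000 trials, true difference zero, one arm affected) agrees:

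| k excluded | Scores discarded | n at 1 week and 1 month | Shift, ρ = 0 | Shift, ρ = 0.5 | Type I error, ρ = 0.5 |
|---|---|---|---|---|---|
| 1 | 2 | 11 | 0 | 0.59 | 5.5% |
| 2 | 4 | 10 | 0 | 1.09 | 6.3% |
| 3 | 6 | 9 | 0 | 1.57 | 7.4% |

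At ρ = 0 the type I error stays at 5.0%. Precision still suffers: power for 10 points falls from 83.3% at 12 per arm to 79.6% at 11 and 75.3% at 10, if subjects are lost from both arms and not replaced.

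**5. Recurrence, conditional on the reading of 7.1.** Assume one recurrence among 12, which is re-treated and leads to discontinuation. The rate goes from 1/12 = 8.3% (exact 95% CI 0.2% to 38.5%) to 0/11 = 0%, with upper limit 1 − 0.025^(1/11) = 28.5%. The intervals overlap widely, but the reported rate becomes zero.

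**6. Would deleting the sentence be enough?** Section 9.8 calls a deviation major if it affects measurement or interpretation of the primary endpoint, and the 6-month POSAS is part of that endpoint. A missed 6-month visit can therefore be classed as major and remove the subject from per-protocol at every visit. Deletion restores n = 12 at the early visits in the full analysis population only.

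**The case against.** The strongest reply is that little hangs on this. The primary and secondary analyses are descriptive, the t-tests are labelled exploratory, and discontinuation is at the investigator's discretion. Contact is attempted after missed visits. Excluding subjects who were never operated on is legitimate: enrolment is at consent, and such subjects have no scar to score. All of this stands, and it limits the weight of the point. It does not remove the contradiction or return the data of an operated subject once discontinued.

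Several stronger inferences are tempting, and the documents do not support them:

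- *Re-treated recurrences will be deleted.* The term alternative treatment is undefined and follows a reason about not having surgery, so it may mean treatment in place of study surgery. Re-treatment of a recurrence is a possible reading, not stated text.
- *A replacement would turn 1/12 into 0/12.* Sections 4.1, 5.1 and 9.6 provide for additional subjects only after death or withdrawal. Whether that covers discontinuation by the investigator is unclear.
- *All safety data on discontinued subjects are lost.* A complication would leave the secondary complication rate. Adverse events are still to be captured (8.2) and tabulated (9.3.4), and whether the exclusion reaches those tables is unclear.
- *The POSAS comparison is seriously biased.* If exactly the most extreme scorers left one arm, the shift would be 1.19, 2.20 or 3.15 points for k = 1, 2 or 3. Nothing in the documents makes that likely.

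**Conclusion.** The point holds in limited form and should be fixed. That 9.1 contradicts itself, and that valid early POSAS scores can be discarded, follows from the text with high confidence. The recurrence consequence is conditional on how 7.1 is read. No size can be taken from the documents, because they give no dropout or recurrence rates. The illustrations assume 1 to 3 exclusions of 12 from one arm only, normal scores and SD 8. On those terms the mean shift is zero if exclusion is unrelated to score and about 0.6 to 1.6 points at correlation 0.5, that is 6% to 16% of the 10-point design difference. A reader might infer that striking out the sentence cures the primary analysis. It does not while per-protocol remains the primary set.

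**What to change.** In 9.1, delete the last sentence and replace the first with: *The full analysis population is all enrolled subjects who had study surgery, using all data observed up to discontinuation.* Then:

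- Use this set for POSAS at each visit, for complications and recurrences (including re-treated ones), and for adverse events. Name it in 9.3.1, 9.3.2, 9.3.4 and 9.5.
- Make it the main summary, with per-protocol as a sensitivity analysis. At the least, report both side by side.
- State in 9.8 that deviations are classified before outcomes are compared by arm.
- Report non-operated subjects in the disposition, and discontinuations and replacements by arm with reasons.

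The cost is small wording changes in 9.1, 9.3, 9.5 and 9.8, with no new data collection. Estimates may move in either direction, and slightly more than 24 subjects may be analysed. Missing 6-month scores stay missing, since no imputation is planned, so the change does not remove any bias from missed 6-month visits.
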